2.2. Eligibility criteria and subgroups

Participants will be identified by specialists in neurology and rehabilitation from inpatients at the Department of Acute Care, Department of Neurology, Thomayer University Hospital or University Hospital Kralovske Vinohrady, Prague, Czech Republic.

Inclusion criteria: Adults (18 - 85 years) after the first ischemic stroke in early sub-acute phase (40, 41), with a slight to moderately severe disability [2 - 4 on the Modified Rankin Scale (42)],

with minimal or moderate motor deficit of upper or lower extremities (on NIHSS Item 5 or 6 scores 1–3 points) who were able to perform activities of daily living prior to stroke event [0 – 2 on the Pre-Stroke Modified Rankin Score (43)], with a potential to accept 4 hours of comprehensive rehabilitation per day and to profit from the physiotherapy. Czech is their native language or its knowledge is at the level of the mother tongue.

Exclusion criteria: Low level of consciousness (vegetative state and/or minimally conscious state); severe cognitive decline that would interfere with administration of the tests, premorbid illiteracy, severe visual and/or auditory deficit that would prevent proper completion of the tests; behavioural disorders and/or lack of cooperation with therapist; and severe medical problems with a poor prognosis, (e.g., severe frailty, advanced and incurable cancer, fracture, cardiovascular disorders as chronic heart failure NYHA III, IV, symptomatic coronary artery disease Angina Severity Class III, IV, respiratory insufficiency as chronic obstructive pulmonary disease GOLD IV, and other severe disease) (44).

Randomisation

All patients meeting the above criteria will be invited to participate and asked to provide a written informed consent. They will be randomly assigned (1:1:1:1) as soon as possible, but always within 48 hours of admission, into one of the four interventions (represented by Group 1, 2, 3 or 4) using offsite-independent randomization protocols (www.randomization.com). Concealed allocation will be performed using sequentially numbered opaque sealed envelopes only accessible by research personnel with no involvement in the trial.

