2.5.2.1. Physical functions and functional independence

Upper extremity functions

• Jamar Hydraulic Hand Dynamometer will be used to measure isometric grip force from 0-90 kg. Five handle positions from 35-87 mm will be tested. The measurement is in kg (the higher the value, the better the function) (77).

• A postural tremor will be measured by the 3-axis accelerometer and 3-axis gyroscope chip (Motion Tracking sensor MPU-6050) which can measure acceleration up to 16 g and rotation up to 2000 degrees per second. The sensor will be fixed to the patient using a ring on a finger during stretching the whole arm forward, separately passed for the left and right hand and with opened and closed eyes (one-minute measurement for each position). Data from the chip will be acquired by an own measuring device with microcontroller Atmel Mega 328 and stored on an SD card.

For the signal analysis, the magnitude of acceleration – the root of sum of each component squares – will be computed from separate axes. The sampling frequency will be 100 Hz. Thus, four signals with 6000 samples will be recorded for each patient – records of postural tremor for right/left hand with opened/closed eyes.

For each record, the signal of acceleration will be filtered by a filter of isoline (typically by high-pass 2^{nd} order Butterworth filter with cut-off frequency of 0.5 Hz). Consequently, the power spectral density (PSD) will be estimated.

The spectral characteristic will be parameterized by selected parameters, for example f_{MAX} (a frequency for which the smoothed PSD is maximal - lower value, lower tremor) or $P_{\text{fl-f2}}$ (a power of the signal in band from f_1 to f_2 - lower value, lower tremor) (78).

- Nine Hole Peg Test is used to measure finger dexterity. A client takes the pegs from a container, one by one, and places them into the holes on the board, as quickly as possible. Shorter times reflect better function (79).
- Action Research Arm Test (ARAT) is a 19 item observational measure to assess upper extremity performance (coordination, dexterity and functioning). Items are categorized into four subscales (grasp, grip, pinch and gross movement). A higher score means better function (80).
- Motor Activity Log is a scripted, structured interview to measure real-world upper extremity function consisted of 14 activities of daily living such as using a towel, brushing teeth, and picking up a glass. A higher score means better function (81).

Mobility and walking

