- Timed Up and Go is a simple performance-based measure of dynamic balance. The subject stands up from a chair, walks 3m, turns back, and sits down again as quickly and safely as possible while being timed. Shorter times reflect better mobility (82).
- Berg Balance Scale is a 14-task scale that requires subjects to maintain their balance in positions and tasks of increasing difficulty. A lower score means worse balance (83).
- The 10 Metre Walk Test is a performance measure used to assess walking speed in meters per second over 10 meters. Shorter time reflects better mobility (84).
- The 6 Minute Walk Test is a long walking capacity test recording the maximal distance a subject can walk at the fastest speed possible in 6 minutes. The more distance covered, the better the walking performance is (84).

Functional Independence

Functional Independence Measure is an 18-item measurement tool which explores an individual's physical, psychological and social function. It uses the level of assistance an

individual needs to grade functional status from total independence to total assistance. The higher the score, the better (higher independence) (85).

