2.7. Descriptive statistics

On the baseline, the distribution of all primary and secondary outcomes will be visualized using histograms and QQ plots. We expect normal distributions in most of the variables defined as raw scores from appropriate tests, or in their log transformations (e. g. tests measuring time needed to walk certain distance or to perform a task). The groups will be compared in their characteristics, primary, and secondary outcomes using the one-way analysis of variance (ANOVA), and its nonparametric version (Kruskal – Wallis test), where needed. The Benjamini-Hochberg correction (97) will be used to account for multiple comparisons. We expect no differences between groups on the baseline. If differences are observed, these will be accounted for in the longitudinal models.

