2.9. Measuring the effectiveness of rehabilitation

To test hypothesis I., i.e., a positive influence on all outcomes, the effect of therapy for each therapeutic group will be assessed separately by paired t-tests performed on pre-test and post-test scores. The Wilcoxon rank test will be used on data where normal distribution cannot be expected.

To test hypotheses II. and III, a comparison between therapeutic groups will be performed using two sample Student t-tests on differences between measurement time points (or Wilcoxon tests respectively for data, where normal distribution of the differences cannot be expected). For hypothesis II, the COMIRESTROKE - ICF group will be compared against the rest of the participants. For hypothesis III, the COMIRESTROKE - NEFI group will be compared against the rest of the participants. A one-sided alternative will be tested according to our hypotheses. We will also implement the one-way ANOVA test to jointly compare all three groups for prepost differences. In addition, a Tukey post-hoc comparison will be made to detect any further group differences beyond our hypotheses.

To assess the overall impact of rehabilitation and to compare effectiveness of different therapeutic approaches for Hypotheses I – III in more complex way, and to test for effect of other covariates in Hypothesis IV, a linear mixed effect model will be used with random patient effect fitted to longitudinal patient data. Measurement effect, group effect and their interaction, as well as effects of other covariates such as the level of disability in admission time will be tested by F test.

To address Goal I, correlations between changes in different examination scores will be evaluated using Pearson correlation coefficient and its nonparametric analogies. A cluster analysis will be performed to identify different phenotypes. This will allow the identification of different groups of patients in relation to the efficacy of the neuro-rehabilitation programs.

To address Goal II, for selected multi-item instruments, item-response theory (IRT) and generalized linear regression models will be used to study differential item functioning with respect to rehabilitation groups. Account will be taken for other respondent characteristics. Use will be made of differential item functioning in change (DIF-C) analysis (7) in order to detect between-group differences.

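### Timed Up and Go, Nine Hole Peg and 10 Metre Walk have no score for a patient unable to do them, so the change tests cannot see recovery from unable to able

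*Combined protocol and SAP*

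**What the plan says.** **Scoring (2.5.2.1).** The Timed Up and Go is performed "as quickly and safely as possible while being timed. Shorter times reflect better mobility (82". In the Nine Hole Peg Test the patient takes the pegs and "places them into the holes on the board, as quickly as possible. Shorter times reflect better function (79". The 10 Metre Walk is "used to assess walking speed in meters per second over 10 meters. Shorter time reflects better mobility (84", so one entry names speed as the measure and then gives the direction of benefit in time.

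**Population (2.2).** Patients enter "with a slight to moderately severe disability [2 - 4 on the Modified Rankin Scale (42", with a limb deficit defined as "on NIHSS Item 5 or 6 scores 1–3 points", in the arm or the leg. Being able to walk, or to use the hand, is not required.

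**Analysis (2.7, 2.9).** Section 2.7 expects log transformation for "tests measuring time needed to walk certain distance or to perform a task". Section 2.9 uses paired tests within each group and, for Hypotheses II and III, "two sample Student t-tests on differences between measurement time points", with Wilcoxon versions as fallback. A mixed model with a random patient effect is added.

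No section gives a ceiling time, zero, worst rank or missing-data rule for a patient who cannot do a test. These outcomes are measured at baseline and three weeks only.

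**The concern.** A time, or its logarithm, has no value for a patient who cannot complete the task. A patient who cannot walk 10 metres at admission and can three weeks later has made one of the larger gains a rehabilitation programme can produce, yet has no difference score. A patient who loses the ability has none either. Without a rule, a programme that restores walking or hand use in more patients gets no credit on these tests, and the arms are compared on subsets defined partly by the outcome itself. Hypothesis I covers all outcomes and Hypothesis III mainly motor functions, so both rely on these measures.

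**Working it through.** **1. Who enters a test on differences, under the text as it stands**

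| Baseline | 3 weeks | Difference in time exists? |
|---|---|---|
| able | able | yes |
| unable | able | no: no baseline time |
| able | unable | no: no later time |
| unable | unable | no |

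The Wilcoxon fallback needs the same two values. Leaving out patients unable at baseline is balanced by randomisation but discards any gain among them. Leaving out those who lose the ability depends on the outcome. In the mixed model a patient who regains the ability contributes a later value only, so which values enter depends on the outcome there too.

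**2. The plan's own figure**

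Section 2.6 gives no figure for the timed tests. Its 70 per group rests on the Berg Balance Scale with d = 0.5, alpha 0.05 and power 0.80: n = 2(1.960 + 0.842)²/0.5² = 62.8, so 63 per group (64 by the t distribution). That does not reproduce 70, and it is a separate matter. For size I take the 210 patients over the four randomised groups: 210/4 = 52.5, or about 52 vs 158 for one arm against the rest.

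**3. Loss from numbers alone**

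If a share f has no difference score, power for one arm vs the rest at d = 0.5, one-sided 5%, is Φ(0.5/SE − 1.645), with SE = √[(1/52.5 + 1/157.5)/(1 − f)].

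- f = 0: SE = 0.159, power Φ(1.49) = 0.93.
- f = 30%: SE = 0.190, power Φ(0.98) = 0.84.
- At f = 10%, 20% and 40%, power is 0.91, 0.88 and 0.78.

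This loss is moderate. The larger problem is what is being estimated.

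**4. What the change score can see (simulation; all inputs assumed)**

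- Latent baseline walking speed is normal with SD 0.45 m/s. A patient is able at 0.10 m/s or more.
- Share unable: mean 0.35 gives Φ((0.10 − 0.35)/0.45) = Φ(−0.56) = 29%; mean 0.55 gives Φ(−1.00) = 16%; mean 0.70 gives Φ(−1.33) = 9%.
- Gain without programme effect: mean 0.15 m/s, SD 0.2.
- Programme effect: either +0.25 m/s in initially unable patients only (at 29% unable, 20% vs 10% of all patients regain walking), or +0.10 m/s in everyone.
- Contrast: 52 vs 158, one-sided 5%, t-test.

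Benefit only in initially unable patients:

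| Share unable | Change in log time | Change in speed, unable = 0 |
|---|---|---|
| 29% | 5–6% | 46% |
| 16% | 5–6% | 23% |
| 9% | 5–6% | 14% |

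The log-time column is the nominal error rate: the test has no ability to detect this benefit at any of the shares tried.

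With +0.10 m/s in everyone, power is 63% for log time against 88% for speed at 29% unable, and 74% against 92% at 9%. The gap narrows only from 88 − 63 = 25 to 92 − 74 = 18 points. Much of it therefore comes from the choice of scale, because the model adds gains in m/s, and not from unable patients.

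**5. Cross-check with a different model**

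Here 10–40% are unable at baseline, 70% of them regain the ability in one arm vs 30% in the rest, and nobody able at baseline benefits. The change-score test rejects 4.7–5.5% of the time. A ranked analysis with still unable worst and regained best rejects 20%, 47%, 72% and 88% of the time at 10%, 20%, 30% and 40% unable. With regain of 50% vs 30%, the ranges are 4.4–5.5% and 11–41%.

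**The case against.** Four points limit the concern, and all stand.

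- **Silence is not a rule.** A reader might infer that the plan drops or penalises these patients. It says neither. Leaving them out is the default result of scoring by time with no provision for inability, and a later rule could prevent it.
- **Blindness is not harm.** A reader might infer that regained function counts against a programme, because those who regain it enter with slow times. That would show in a comparison of three-week times alone, which section 2.9 does not plan. A random-intercept group-by-visit model fitted to the unable-only scenario (52 vs 158, 150 trials) gave a mean interaction of +0.003 log units (average SE 0.076), with 6% of trials significant in the harmful direction at a nominal 5%.
- **Hypothesis III does not rest on these tests alone.** It covers secondary outcomes, mainly motor. ARAT, Berg and FIM can register inability as a low score, and the 6 Minute Walk can take 0 m. If the 10 Metre Walk is analysed as speed, it too has a natural zero.
- **The rate is unknown.** Section 2.2 also asks for a minimal or moderate deficit and the potential to accept four hours of rehabilitation a day. An arm deficit need not prevent walking, nor a leg deficit peg placement. That some patients are unable is an inference from mRS 4 and a limb score of 3.

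None of this supplies a score for inability on the three tests.

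**Conclusion.** The point holds for three secondary outcomes: the Timed Up and Go, the Nine Hole Peg Test and, if analysed as time, the 10 Metre Walk. Followed as written, the tests on differences cannot see recovery from unable to able, and they omit patients who lose the ability. The blindness follows from the scoring and does not depend on the assumed rate; how much it costs does. For a benefit confined to initially unable patients, the illustration puts the cost at 5–6% power against 14–46%, over an assumed 9–29% unable. The documents do not support a claim that Hypothesis III as a whole is mis-measured. This should be corrected, but it does not undermine the trial.

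**What to change.** In sections 2.5.2.1 and 2.9, before outcomes by group are seen:

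- Analyse the 10 Metre Walk as speed in m/s with unable = 0, which also settles the conflict between time and speed. Score the 6 Minute Walk as 0 m when unable.
- For the Timed Up and Go and Nine Hole Peg Test, give inability the worst value, either as a rate with zero (1/time, pegs per second) or as a worst rank. If ranks are used on change, state where a patient unable at both visits falls. Use the Wilcoxon test already planned.
- Keep every patient assessed at both visits in the within-group and between-group tests.
- Record unable separately from not done in the eCRF; the distinction may not be recoverable later.
- Report by arm the proportion moving from unable to able and from able to unable.

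The cost is endpoint wording and one eCRF code. The units are less familiar than seconds, and there is a spike at zero. The rank test gives up little: in a two-arm version of the simulation (52 vs 52, two-sided 5%, 29% unable, 0.10 m/s gain in all), power was 57% against 62% for the t-test on speed.

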2.5.2.2. Speech and swallowing

The Gugging Swallowing Screen is a simple stepwise bedside screen that allows a graded rating with separate evaluations for nonfluid and fluid nutrition starting with nonfluid textures. It assesses the severity of aspiration risk. A higher score means better function (85).

The 3F Test – Dysarthric Profile consists of three subtests (Faciokinesis, Phonorespiration, Phonetics). The overall Index of Dysarthria (ID) is a sum of 45 items with the maximum score of 90 (the best function) (86).

Following the previously published guideline (87), the dysarthria assessment is based on the automatic evaluation of utterances, including sustained phonation, speech diadochokinetic task, and connected speech. Utterances will be recorded during the sessions with speech language pathologist. The recording will take place in a quiet room with low ambient noise using a head-mounted condenser microphone (Shure Beta 53, Niles, Illinois, U.S.), placed approximately 5cm from the mouth corner at an angle of 70°. The recordings will be sampled at 48kHz with 16bit resolution. The automatic analysis will be performed using the beta version of the freely available Dysarthria Analyzer (Czech Technical University in Prague, available at http://dysan.cz/).

The Mississippi Aphasia Screening Test (MAST) was developed as a brief, repeatable screening measure for individuals with severely impaired communication/language skills. It has nine subtests that range from 1 to 10 items per subscale. The Index scores sum to 50 points each and are added for the MAST Total Score (0 -100 points). The higher the score, the better function (88).

Image Naming Test (Test pojmenování obrázků, TPO) is a test of confrontational naming of nouns and verbs. Words are selected based on success, frequency of occurrence, age of adoption, length, and visual complexity. The maximum sum is 60 points (30 verbs and 30 nouns), the results can be assessed qualitatively according to the type of unexplained words (89).

2.5.2.3. Cognitive and psychological functions

The Montreal Cognitive Assessment (MoCA) is an assessment for detecting cognitive impairment ranged between 0 and 30 points. The more the better. The Czech version was validated and cut-offs and norms were established (90, 91).

The Amnesia Light and Brief Assessment (ALBA) is an original Czech and innovative test to assess more cognitive functions (therefore Assessment in the name) including memory (therefore Amnesia) easily (therefore Light) and quickly in three minutes (therefore Brief). The ALBA consists of four tasks: (1) repetition and encoding of a six-word sentence "Indian Summer Brings First Morning Frost", (2) sequential demonstration of six gestures and (3) their immediate recall, and (4) final recall of the original sentence. The first task of a sentence repetition reflects (1) language (impaired in aphasia) or (2) encoding and working memory (impaired in memory and attention deficits). The second task of gesturing can be impaired as a result of sensory aphasia or apraxia. Short-term and episodic memory is measured in two different ways, (1) in the third part of the ALBA, i.e., incidental memory of the gestures, and

(2) in the fourth part, i.e., intentional verbal memory of the sentence. Overall memory can be expressed as the ALBA score, which is a sum of correctly recalled sentence words and gestures. The higher scores of each ALBA part the better function. Scores of individual parts range from 0 (the worst) to 6 points (the best) for each of four tasks: (1) the number of correctly repeated words of the sentence (Word 1 score: 0-6 points), (2) the number of correctly recalled words of the sentence after the distraction using the TEGEST (W2 score: 0-6), (3) the number of correctly performed gestures of the TEGEST (Gesture 1 score: 0-6), and (4) the number of correctly recalled gestures of the TEGEST (G2 score: 0-6). The sum, called ALBA score, is derived from correctly recalled words of the sentence and correctly recalled gestures together (W2 + G2: 0-12 (6 + 6)). Example scores of the ALBA test can be the following: 5/1 + 5/3 (W1/2 + G1/2) that gives a total ALBA score: 4 (1 + 3) points (92, 93).

Picture naming and immediate recall (PICNIR) is an original Czech and brief test which is a method certified by Ministry of Health of the Czech Republic in 2017. The purpose of the PICNIR is to evaluate written speech, long-term sematic and short-term visual memory simultaneously and quickly in five minutes. The test consists of two parts. The task of an examinee is to write down names of 20 black and white pictures in one word and remember them at the same time. Then they are asked to rewrite as many picture names as they can recall during one minute. The results of the PICNIR include a number of wrongly named or unnamed pictures in the first naming part and a number of correctly recalled picture names in the second recall part. The less naming errors and more recalled picture names the better (94).

Neuro - QOL depression is a self-report of health-related quality of life in domain concerning depression (95). (72)

2.5.3. Other Pre-specified Outcome Measures - molecular biological readouts of rehabilitation

Blood will be taken for total RNA extraction, cDNA synthesis and real-time QPCR assessment of lncRNA candidates previously identified as potential therapeutic influencers in ischemic stroke. Whole blood will be collected from fasting patients for RNA analysis. A RiboPureTM-Blood Kit (cat# AM1928, ThermoFisher Scientific) will be used for isolating high-quality RNA directly from whole blood. This kit contains an RNA*later*® Solution (cat.# AM7020, ThermoFisher Scientific) that protects RNA and is designed to eliminate the need to process samples as soon as they are harvested. RNA*later*® Solution also "freezes" the gene expression profile of the cells. Treated samples can be safely stored at ambient temperature for extended periods of time (up to three days or more). Blood samples stored in RNA*later*® Solution yield RNA of comparable quality to blood samples processed directly according to the commercial website. Expected average yields of total RNA will be between 2–4 µg/0.5 mL of whole blood. Total RNA will be reverse transcribed into cDNA. Human lncRNA and internal endogenous gene (eg. *GAPDH*) expression will be quantified using RNA extracted from blinded samples (ie. concealment of group allocation) to eliminate bias.

